3 STATISTICAL ANALYSES

3.1 GENERAL CONSIDERATIONS

In general, continuous data will be summarized using the number of observations available, mean, standard deviation (SD), median, interquartile range (Q1, Q3), minimum, and maximum.

Categorical and ordinal data will be summarized using the count and percentage of participants.

Efficacy data will be analyzed in the randomized and treated population except the primary endpoint which will be analyzed in the mITT population, and safety data will be analyzed in the safety population, unless specified otherwise.

In Part A, baseline values are defined as follows. The baseline value of NfL is defined as the lower value of screening and Day 1 visits if the number of gd-enhancing T1 lesion at Day 1 is greater than zero, otherwise it will be the average values of the assessments on screening and Day 1 visits prior to the first dose of the study intervention. The baseline values of EDSS and PD biomarkers other than NfL are defined as the average of the screening and Day 1 visit values prior to the first dose of the study intervention. If one of the values for the above assessments at screening and Day 1 is missing, the non-missing value will be used as the baseline value. For the other efficacy and safety assessments, the baseline values are defined as the last available value before the first dose of the study intervention. For the C-SSRS, the baseline value will be the worst assessment between the past 6 months evaluation at screening and the since last visit evaluation on Day 1. For participants randomized but not treated, the baseline value is defined as the last available value before randomization. Unless otherwise indicated, 2-sided p-values and 95% confidence intervals [CI(s)] will be provided for efficacy assessment of treatment differences. Unless otherwise specified, analyses will be performed by initial intervention group, ie, placebo or SAR443820 20 mg QD (and overall for baseline and demographics characteristics).

In Part B, efficacy analyses will be conducted accumulatively according to the treatment group allocated by randomization in Part A (ie, placebo/SAR443820 20 mg QD versus SAR443820 20 mg QD/ SAR443820 20 mg QD). Baseline values defined above for Part A will be used as the baseline in the efficacy analyses for Part B, unless otherwise noted. Safety analyses in Part B are specified in [Section 3.6](#).

Observation period

The observation period for safety will be divided into 4 segments:

- The **pre-treatment period** is defined as the period up to first IMP administration.
- The **on-treatment period** (ie, treatment-emergent (TE) period) **for the Part A** is defined as the period from the first IMP administration to the earliest of 1) last IMP administration + 14 days, 2) first IMP in Part B, 3) death date, or 4) last contact date.
- The **on-treatment period** (ie, treatment-emergent (TE) period) **for the Part B** is defined as the period from the first IMP administration in Part B to the earliest of 1) last IMP administration + 14 days, 2) death date, or 3) last contact date.
- The **post-treatment period**, if applicable, is defined as the period from the end of the on-treatment period to the last contact date.

The on-study period is defined as the time from randomization until the end of the study defined as the last scheduled visit for those who completed the study and the end-of-study date collected on electronic case report form (e-CRF) page “Completion of End of Study” for those who did not complete the study. If death is the end-of-study reason, date of death will be used.

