8.1.1 Serum neurofilament response

Serum NfL will be collected as part of the blood specimen according to the SoA, with the mean of the screening and Day 1 predose sample levels serving as the baseline value for calculating NfL changes. sNfL samples will serve as the primary endpoint for the duration of the study in Parts A and B.

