9.2.1 General considerations

The baseline value is defined as the last available value before the first dose of double-blind IMP, except otherwise specified. For participants randomized but not treated, the baseline value is defined as the last available value before randomization/enrollment.

Unless otherwise specified, analyses will be performed by initial intervention group, ie, placebo or SAR443820 20 mg QD (and overall, for baseline and demographics characteristics).

The observation period will be divided into 4 segments:

- The **pre-treatment** period is defined as the period up to first IMP administration.
- The **treatment-emergent (TE) period** is defined as the period from the first IMP administration to the last IMP administration + 14 days. The TE period includes the following 2 periods:
 - The **on-treatment period** is defined as the period from the first IMP administration to the last administration of the IMP + 1 day.
 - The **residual treatment period** is defined as the period from the end of the on-treatment period to the end of the TE period.
- The **post-treatment period** is defined as the period from the end of the TE period.

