1	12-Jul-2024	
This version of SAP includes the following changes compared to the amended protocol 04:
 
For the analysis of sNfL, replace baseline MS type (RMS versus PMS) with the randomization stratification factor MS clinical subtype (RRMS, SPMS, or PPMS) in the MMRM model and exclude MS type by visit interaction from the covariates. For the analyses of new Gd-enhancing T1 lesions and new/enlarging T2 lesions, replace baseline MS type (RMS versus PMS) with the randomization stratification factor MS clinical subtype (RRMS, SPMS, or PPMS) in the negative binomial model.Remove the endpoints 'change from baseline in the total number and volume of non-enhancing lesions at Weeks 12, 24, 36, and 48' for Part A and 'change from baseline in the total number and volume of non-enhancing lesions at Week 96' for Part B as data for these endpoints were not collectedRemove the endpoints 'change from baseline in the intensity (T1) of slowly expanding lesions at Weeks 12, 24, 36 and 48' for Part A and 'change from baseline in the intensity (T1) of slowly expanding lesions to Week 96' for Part B as data for the corresponding endpoints were not collected.Change the confirmation period of time-to-event endpoints in Part B (ie, time to CDP, time to 20% increase in 9-HPT, time to 20% increase T25-FW test, and time to CCDP) from 12 weeks to 24 weeks.	Clarification

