3.2.2 Main analytical approach

3.2.2.1 Part A

The primary endpoint in Part A will be analyzed with the primary estimand defined according to the following attributes:

- Endpoint: sNfL levels at Week 48 relative to baseline
- Treatment condition: SAR443820 will be compared to placebo, on top of background therapy where applicable
- Analysis population: mITT population
- Intercurrent events (IE):
 - The IMP discontinuation IE will be handled with the hypothetical strategy. The primary endpoint will be assessed based on assessments performed before IMP discontinuation.
 - The modification in the background DMT (either dosage or medication) IE will be handled with the hypothetical strategy. The primary endpoint will be assessed based on assessments performed before the permanent modification of the background DMT (as distinguished from rescue therapy, which is intermittently limited to 2 to 5 days, after which the original background DMT will be restored at its pre-rescue dose).
- Population-level summary: ratio of the geometric mean ratios compared to baseline between intervention groups.

The primary analytical approach will use a mixed effect model with repeated measures (MMRM) on natural (base ‘e’) log-transformed sNfL levels. The model will include the fixed categorical effects of the treatment group (SAR443820 or placebo), MS clinical subtype (RRMS, SPMS, or

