PPMS), visit (Weeks 12, 24, 36, 48), treatment-by-visit interaction, log-transformed baseline sNfL levels and log-transformed baseline sNfL levels-by-visit interaction. An unstructured covariance structure will be used to model the within-subject errors. The Kenward-Roger (1) approximation will be used to estimate denominator degrees of freedom and adjust standard errors. Missing data will be handled by MMRM under the missing at random (MAR) assumption. The geometric mean ratios of sNfL levels at Week 48 relative to baseline in each treatment group, as well as the ratio of the geometric mean ratios under treatment with SAR443820 compared to placebo will be estimated (point estimates and 2-sided 90% confidence intervals [CI], respectively) from the MMRM model using weights for each stratum equal to the overall proportion of participants in each stratum (ie, “population weight”) through exponentiated least squared means and exponentiated least squared means differences. Plots of geometric mean ratios of sNfL levels relative to baseline in each treatment group with 90% CIs over time will be provided.

If this MMRM model fails to converge, the following variance-covariance structures will be tested in this order:

- Heterogeneous Toeplitz
- Heterogeneous AR(1)
- Heterogeneous CS
- Toeplitz
- AR(1)
- CS.

The first (co)variance structure yielding convergence will be used as the primary analysis. When a variance-covariance structure other than unstructured is used, the denominator degree of freedom will be estimated using the between within method (DDFM=BW in SAS PROC MIXED) (2)

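### SAP 3.1 changes the baseline sNfL rule for participants with enhancing lesions without listing the change, and the primary model does not adjust for lesion status

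*SAP*

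**What the plan says.** Protocol 9.2.1 sets a general default: "The baseline value is defined as the last available value before the first dose of double-blind IMP, except otherwise specified". For sNfL, Protocol 8.1.1 does specify otherwise, "with the mean of the screening and Day 1 predose sample levels serving as the baseline value for calculating NfL changes", and makes no exception for lesion status.

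SAP 3.1 reads: "The baseline value of NfL is defined as the lower value of screening and Day 1 visits". This applies only to participants whose Day 1 scan shows at least one enhancing T1 lesion; all others get the average of the two samples. No reason is given. If one of the two samples is missing, the other is used. The other pharmacodynamic biomarkers keep the plain average. The same baseline carries into the Part B efficacy analyses.

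The SAP version history introduces its list with "This version of SAP includes the following changes compared to the amended protocol 04". The items are the MS subtype covariates, removed imaging endpoints and the Part B confirmation period. The sNfL baseline is not among them.

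Baseline enters the primary analysis in two ways (SAP 3.2.2.1). It is a covariate, as "log-transformed baseline sNfL levels and log-transformed baseline sNfL levels-by-visit interaction", and it is the denominator of reported results, "The geometric mean ratios of sNfL levels at Week 48 relative to baseline in each treatment group", given with 90% CIs and plotted. The primary summary is the "ratio of the geometric mean ratios compared to baseline between intervention groups". Gd status is not a term in this model.

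**The concern.** The baseline of the primary endpoint differs between the two documents, and a reader of the change list would not know it. The lower of two noisy values is on average below their mean. Under the SAP, baseline therefore means one thing in Gd-positive participants and another in everyone else.

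The within-arm ratios are at stake. They are reported for each arm, and they matter most in Part B, where all participants receive SAR443820 and durability is read against baseline without a concurrent placebo arm.

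The rule also implies that Day 1 lesion status carries information about sNfL. The model uses that information only to choose between two baseline values. Participants who cannot receive contrast may enrol (Protocol 5.2, note to E 18), and the rule does not name them.

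**Working it through.** **Inputs.** From the documents: the two baseline rules, 168 participants randomized 1:1, 17% dropout, a 30% reduction (GMR 0.70) and a target upper limit of 0.90. Not in the documents, so assumed and varied: the within-person log SD (s), the Gd-positive share (p), and the size and timing of any lesion-related rise in sNfL.

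**The plan's own figure.** 139/0.83 = 167.5, which rounds up to 168, so about 70 per arm are evaluable. The target needs a log-scale half-width of at most ln(0.90/0.70) = 0.251. At 70 per arm with the 90% width probability, this holds for a log SD up to about 0.83. The planning SD is redacted, so the figure can be neither confirmed nor refuted. The stated basis does not use the baseline definition, so N does not depend on this point.

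**Direction.** The lower of two values never exceeds their mean. Each affected participant's ratio to baseline can only rise or stay the same relative to the protocol rule.

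**Size with no lesion-related rise.** For two exchangeable log values, E[min] = mean - s/sqrt(pi).
- s = 0.15: shift 0.085, factor exp(0.085) = 1.09 in Gd-positive participants.
- s = 0.30: shift 0.169, factor exp(0.169) = 1.18.
- Whole arm, factor exp(p x shift): exp(0.10 x 0.085) = 1.009 to exp(0.30 x 0.169) = 1.052, that is about 1-5%.

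The protocol averages the levels themselves, which lies slightly above the log-scale mean. Against that rule the Gd-positive shift at s = 0.20 is 13% rather than 12%.

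**Simulation.** A single-visit ANCOVA stands in for the Week 48 contrast, with 140 participants, 1,500 replicates per setting, true placebo ratio 1.00 and true GMR 0.70. Any lesion-related rise is on Day 1 only and is gone by Week 48.

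| s | p | Day 1 rise (log) | Placebo ratio: mean / lower value | GMR: mean / lower value | SE: mean / lower value |
|---|---|---|---|---|---|
| 0.2 | 10% | 0 | 0.9893 / 1.0015 | 0.7002 / 0.7002 | 0.0722 / 0.0726 |
| 0.2 | 30% | 0 | 0.9897 / 1.0265 | 0.7006 / 0.7010 | 0.0721 / 0.0730 |
| 0.4 | 30% | 0 | 0.9635 / 1.0420 | 0.6983 / 0.6989 | 0.0999 / 0.1020 |
| 0.2 | 30% | 0.4 | 0.9259 / 0.9950 | 0.7007 / 0.7003 | 0.0739 / 0.0729 |

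The GMR stayed at 0.696-0.703 under both rules in every setting run. With no rise, the SE under the lower-value rule was at most about 2% larger (0.1020/0.0999 = 1.021). With the Day 1 rise of 0.4 it was slightly smaller.

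If both samples are raised by 0.4 (s = 0.2), a true ratio of 1.00 in Gd-positive participants is estimated as 0.664 with the mean and 0.750 with the lower value. Neither rule recovers the stable level.

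**Gd status in the model.** Across 72 combinations of assumed inputs, residual variance relative to the SAP rule without Gd status was:
- lower-value baseline plus Gd status: 0.70-1.00;
- log-scale mean plus Gd status: 0.69-0.995;
- log-scale mean without Gd status: up to 1.13, so it can be worse.

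With Gd status in both models, the mean gave 0.96-0.996 of the variance under the lower-value rule. That adding a covariate never raises large-sample residual variance is true by construction. The real cost is up to two degrees of freedom out of about 139 evaluable participants.

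**The case against.** The best defence is that the lower-value rule has a sensible purpose. Protocol 4.2 aims to capture chronic neuroaxonal damage in stable participants. If an active lesion raises sNfL on Day 1 and the effect fades, the lower value is nearer the stable level and the protocol mean is the one that misleads (0.995 against 0.926 above, truth 1.00). This stands as a possibility. A reader might infer from the algebra that the SAP's within-arm ratios are simply too high. The documents do not support that, because the upward shift is established only relative to the protocol mean. Equally, the SAP never states this purpose, and the rule only partly works when both samples are raised.

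It is also fair that a Gd covariate is a separate matter from the baseline definition and does not settle the within-arm ratios. It helps the treatment comparison; the ratios still depend on which baseline is used.

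A reader might also infer that post-baseline sNfL needs matching treatment when new Gd lesions appear. It does not. Those lesions are post-randomization outcomes and a secondary endpoint, so correcting for them could remove treatment effect. Each later scheduled visit also has only one sNfL sample.

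Finally, SAP 3.2.3 (sensitivity analysis) is redacted and may already include an alternative baseline. Part B is labelled descriptive.

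**Conclusion.** The documents conflict on the baseline of the primary endpoint, and the SAP's change list omits it. Relative to the protocol rule, the SAP raises the within-arm ratios by about 1-5% per arm, assuming s of 0.15-0.30, 10-30% Gd-positive and no lesion-related rise. Whether that is bias cannot be settled from the documents, since it turns on how active lesions affect sNfL.

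Two stronger inferences fail. The primary between-arm ratio is not biased under either rule, because both samples and the Day 1 lesion status precede treatment and the rule is the same in both arms. Nor is there evidence of a data-driven change: the SAP states that it was approved before the first database lock.

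What remains is an undeclared departure that should be reconciled, and a prognostic variable already collected that the primary model as written leaves out.

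**What to change.** 1. Add Day 1 Gd-lesion status (0, 1 or more, not assessed) as a fixed effect in the primary MMRM. Under the assumed inputs this never increases residual variance and can reduce it. The cost is one covariate with a small not-assessed category, and no new data.
2. Reconcile SAP 3.1 with Protocol 8.1.1, give the reason for the rule chosen, and list the difference in the change table. With Gd status in the model, the mean is slightly more efficient. Reverting to the mean without Gd status is not recommended, because it can be less efficient than the present rule. If averaging is to be on the log scale, say so, since the protocol averages the levels.
3. Report the within-arm ratios, in Part A and Part B, under both baseline definitions, one as primary and the other as a sensitivity analysis, unless the redacted section 3.2.3 already does so. This costs SAP wording and one extra set of output.

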3.2 PRIMARY ENDPOINT(S) ANALYSIS

The primary endpoint in Part A detailed in this section is sNfL levels at week 48 relative to baseline.

The primary endpoint in Part B detailed in this section is sNfL levels at week 96 relative to baseline.

3.2.1 Definition of endpoint(s)

The primary endpoint in Part A and Part B is based on NfL levels measured in serum (sNfL). For Part A, the principal time point is Week 48. For Part B, the principal time point is Week 96.

3.2.2 Main analytical approach

3.2.2.1 Part A

The primary endpoint in Part A will be analyzed with the primary estimand defined according to the following attributes:

- Endpoint: sNfL levels at Week 48 relative to baseline
- Treatment condition: SAR443820 will be compared to placebo, on top of background therapy where applicable
- Analysis population: mITT population
- Intercurrent events (IE):
 - The IMP discontinuation IE will be handled with the hypothetical strategy. The primary endpoint will be assessed based on assessments performed before IMP discontinuation.
 - The modification in the background DMT (either dosage or medication) IE will be handled with the hypothetical strategy. The primary endpoint will be assessed based on assessments performed before the permanent modification of the background DMT (as distinguished from rescue therapy, which is intermittently limited to 2 to 5 days, after which the original background DMT will be restored at its pre-rescue dose).
- Population-level summary: ratio of the geometric mean ratios compared to baseline between intervention groups.

The primary analytical approach will use a mixed effect model with repeated measures (MMRM) on natural (base ‘e’) log-transformed sNfL levels. The model will include the fixed categorical effects of the treatment group (SAR443820 or placebo), MS clinical subtype (RRMS, SPMS, or

PPMS), visit (Weeks 12, 24, 36, 48), treatment-by-visit interaction, log-transformed baseline sNfL levels and log-transformed baseline sNfL levels-by-visit interaction. An unstructured covariance structure will be used to model the within-subject errors. The Kenward-Roger (1) approximation will be used to estimate denominator degrees of freedom and adjust standard errors. Missing data will be handled by MMRM under the missing at random (MAR) assumption. The geometric mean ratios of sNfL levels at Week 48 relative to baseline in each treatment group, as well as the ratio of the geometric mean ratios under treatment with SAR443820 compared to placebo will be estimated (point estimates and 2-sided 90% confidence intervals [CI], respectively) from the MMRM model using weights for each stratum equal to the overall proportion of participants in each stratum (ie, “population weight”) through exponentiated least squared means and exponentiated least squared means differences. Plots of geometric mean ratios of sNfL levels relative to baseline in each treatment group with 90% CIs over time will be provided.

If this MMRM model fails to converge, the following variance-covariance structures will be tested in this order:

- Heterogeneous Toeplitz
- Heterogeneous AR(1)
- Heterogeneous CS
- Toeplitz
- AR(1)
- CS.

The first (co)variance structure yielding convergence will be used as the primary analysis. When a variance-covariance structure other than unstructured is used, the denominator degree of freedom will be estimated using the between within method (DDFM=BW in SAS PROC MIXED) (2)

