3.1 APPROPRIATENESS OF MEASUREMENTS

3.1.1 Measurements for efficacy assessment

A hallmark feature of MS that correlates highly with disability is axonal damage and loss, which has been associated with brain atrophy, the ultimate diagnostic evidence of disease progression and plays a key role in long-term disability (8, 9). This axonal damage manifests in CSF, plasma and serum in the form of neurofilaments (heavy and light chain) that are lost as part of the neurodegenerative process in a range of neurological diseases (10). In some cases of progressive MS, elevated neurofilament has been reported as the only evidence of disease (16). Neurofilament light chain levels have been demonstrated in studies to be predictive of disease course and are responsive to DMTs in MS (11); therefore, serum neurofilament is chosen as the primary endpoint in this trial.

Measurement of delay of disability progression is an important clinical endpoint and is endorsed by regulatory guidance (17). The EDSS is widely used to measure neurological disability in clinical trials and routine settings (18). Due to the known fluctuation in EDSS scores, CDP confirmed after 12 and 24 weeks is used as an endpoint in clinical trials of progressive MS (19, 20).

Due to the limited sensitivity of the EDSS to changes in upper limb function and early gait symptoms, the timed 25-foot walk test (T25-FW) test and the 9-hole peg test (9-HPT) were added to the EDSS, making a composite endpoint, the EDSS-Plus (13). The EDSS-Plus is used as a secondary endpoint to attempt a more sensitive measurement for efficacy evaluation.

MRI markers of inflammatory activity in the brain observed in previous clinical trials of progressive MS (19, 20) and RMS will be measured. The number of new Gd-enhancing T1 hyperintense lesions will be used as a secondary endpoint, as accumulation of Gd contrast agent in brain tissue is related to inflammatory activity in MS patients. Also, the number of new T2-hyperintense lesions and change in their volume are included as secondary endpoints, as they reliably reflect accumulating MS lesion load over time. Additional MRI measurements include change in brain volume, slowly expanding/evolving lesions, and phase rim lesions, which are considered to be markers of the CNS degenerative process and are therefore assessed to inform on SAR443820's effect on disease progression.

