4.2 SCIENTIFIC RATIONALE FOR STUDY DESIGN

This is a Phase 2 proof-of-concept study for which a double-blind, randomized, placebo-controlled design has been selected to minimize possible biases in the study outcome.

Male and female participants with a diagnosis of RRMS, SPMS or PPMS between 18 and 60 years inclusive will be selected for this study. The age range is limited to participants \leq 60 years to increase the probability of response to treatment and reduce potential confounding from age-related neurofilament elevations. Participants enrolled in this study will be under stable conditions (absence of clinical relapse in the 8 weeks prior to screening) to capture the effect of treatment on chronic neuroaxonal damage reflected in sNfL levels, particularly because the mechanism of SAR443820 modifies disease pathology, rather than symptomology.

Part A of this study is a randomized double-blind, placebo-controlled design, while Part B is an open-label long-term extension during which neurofilament, imaging, clinical and safety data will be collected to characterize the long-term treatment effects of SAR443820.

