3.2.5 Subgroup analyses for primary endpoint in Part A

To assess the homogeneity of the treatment effect across various subgroups, analyses will be performed on the primary endpoint in Part A across the following subgroups (categories with fewer than 10% participants will be combined with other categories; for factors with only two categories, no subgroup analysis will be performed if fewer than 10% participants in one category):

- MS clinical subtypes
 - RRMS, SPMS, PPMS
 - Pooled RMS (relapsing SPMS + RRMS), non-relapsing SPMS, PPMS
 - Pooled RMS (relapsing SPMS + RRMS), pooled PMS (non-relapsing SPMS + PPMS)
- Background DMT (with concomitant DMT, without concomitant DMT)
- Age at screening (<50, \geq 50 years)
- Sex (Male or Female)
- Baseline BMI (<median, \geq median), median value refers to the median baseline BMI among all randomized participants.
- Baseline EDSS score (<4, \geq 4)

The estimated geometric mean ratio in each treatment group (ie, SAR443820 versus placebo) and the relative reduction under treatment with SAR443820 compared to placebo will be provided (point estimates and 2-sided 90% confidence intervals [CI], respectively) for each subgroup separately, using the same method as specified in [Section 3.2.2.1](#) for the main analysis of the

primary endpoint in Part A. Forest plots of geometric mean ratio and corresponding 90% CIs comparing SAR443820 to placebo within each subgroup will be provided.

Treatment by subgroup interaction and its p-value will be derived from a MMRM with terms for treatment, MS clinical subtypes (RRMS, SPMS, or PPMS), visit (Weeks 12, 24, 36, 48), treatment-by-visit interaction, log-transformed baseline sNfL levels, log-transformed baseline sNfL levels-by-visit interaction, subgroup (if different than the aforementioned covariates), and subgroup-by-treatment interaction as covariates. If a quantitative subgroup by treatment interaction is detected with nominal p-value < 0.1 for any subgroup factor, a further investigation will be performed to evaluate possible qualitative interaction.

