5.3 APPENDIX 3 DEMOGRAPHICS AND BASELINE CHARACTERISTICS, PRIOR OR CONCOMITANT MEDICATIONS

Demographics, baseline characteristics, medical surgical history

The following demographic and baseline characteristics, smoking and alcohol history, disease characteristics at baseline, and medical and surgical history will be summarized using descriptive statistics in the randomized population.

Demographic and baseline characteristics:

- age in years as a quantitative variable and in categories (≤ 40 , > 40)
- sex (Male, Female)
- race (White, Black or African American, Asian, American Indian or Alaska Native, Native Hawaiian or Other Pacific Islander, Multiple, Unknown, Not reported)
- ethnicity (Hispanic or Latino, Not Hispanic or Latino, Unknown, Not reported)
- weight in kg as a quantitative variable
- BMI in kg/m² as a quantitative variable and in categories (< 25 , ≥ 25 to < 30 , ≥ 30)

Smoking and alcohol habits:

- smoking history (Never, Current, Former)
- cessation prior to screening for Former smokers in months
- cigarettes per day for smokers
- frequency of alcohol drinking in the past 12 months (Never, Occasional, At least monthly, At least weekly, At least daily)
- Number of standard alcohol drinks on typical day when drinking (1 or 2, > 2)

Disease characteristics at baseline:

- MS type (PPMS, SPMS non relapsing, SPMS relapsing, RRMS)
- time since symptom onset in years
- time since diagnosis in years as a quantitative variable and in categories (< 1 , ≥ 1 to 5 , ≥ 5 to 10 , ≥ 10)
- time since most recent relapse in years
- number of relapses within the past 1 year as a quantitative variable and in categories (0, 1, 2, ≥ 3)
- number of relapses within the past 2 years as a quantitative variable and in categories (0, 1, 2, ≥ 3)
- baseline EDSS score as a quantitative variable

- time since most recent MRI prior to screening in months
- number of active Gd-enhancing T1 lesions on last MRI prior to screening as a quantitative variable and in categories (0, 1, 2, ≥ 3)

Baseline safety and efficacy parameters (apart from those listed above) will be presented along with the safety and efficacy summaries.

Relevant medical (or surgical) history collected in the eCRF will be coded to a LLT, PT, HLT, HLGT, and associated primary SOC using the MedDRA version currently in effect at Sanofi at the time of database lock and will be summarized by primary SOC and HLT (internationally agreed SOC order and decreasing frequency of HLTs in the Overall group).

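### Adding age and baseline DMT use to the primary sNfL MMRM is a cheap, low-severity improvement, likely to narrow the 90% CI slightly and make the MAR assumption more credible

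*SAP*

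**What the plan says.** SAP 3.2.2.1 gives the primary model in one sentence. It opens "The model will include the fixed categorical effects of the treatment group (SAR443820 or placebo), MS clinical subtype (RRMS, SPMS, or" PPMS) and continues with "visit (Weeks 12, 24, 36, 48), treatment-by-visit interaction, log-transformed baseline sNfL levels and log-transformed baseline sNfL levels-by-visit interaction". No other covariate is listed. Randomisation is stratified by MS clinical subtype only (SAP 1.1, Protocol 6.3).

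On age, Protocol 4.2 sets the upper limit of 60 years partly to "reduce potential confounding from age-related neurofilament elevations". Participants aged 18 to 60 still enter (Protocol 5.1).

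On DMT, Protocol 3.1.1 says that NfL levels "are responsive to DMTs in MS (11"). Protocol 5.1 admits both untreated participants and those stable for at least 3 months on an allowed DMT.

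Both variables are on file. SAP 5.3 summarises "age in years as a quantitative variable and in categories", and Protocol 6.8 requires medication in use at enrolment to be recorded.

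Both are also subgroup factors for the primary endpoint in SAP 3.2.5: "Background DMT (with concomitant DMT, without concomitant DMT") and "Age at screening (<50" against 50 years and over). The interaction model there adds "subgroup (if different than the aforementioned covariates), and subgroup-by-treatment interaction as covariates", so each enters as a main effect, one factor at a time.

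SAP 3.2.3, the sensitivity analysis for this endpoint, is redacted.

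**The concern.** The trial is sized on the width of the 90% CI for the sNfL ratio (Protocol 9.4, SAP 4), so precision is its design criterion. A covariate that predicts Week 48 sNfL beyond the terms already fitted narrows that interval and removes the effect of a chance imbalance in that covariate. The plan names two candidates, collects both, and uses neither in the main model. The visible text gives no reason.

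There is a second consideration. The primary estimand drops sNfL data after IMP discontinuation or permanent DMT modification and relies on MAR (SAP 3.2.2.1). Protocol 6.8 says that stopping, re-dosing or switching a DMT in Part A leads to IMP discontinuation. Participants on a DMT therefore have a route to censoring that untreated participants largely lack. If DMT status also relates to later sNfL, MAR is easier to defend with DMT status in the model.

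**Working it through.** **1. The plan's own sizing.** Inputs: 168 randomised and 17% dropout (Protocol 9.4, SAP 4); a 30% reduction, so GMR 0.70 (Protocol 9.4); upper 90% limit below 0.90 (SAP 4). The SD in Table 7 is redacted, so the figure cannot be fully reproduced. What can be checked:
- Evaluable participants: 168 x 0.83 = 139.4, taken as 70 per arm.
- Largest allowed half-width on the log scale: ln(0.90/0.70) = 0.2513.
- Largest compatible SD = 0.2513 / (1.645 x sqrt(2/70)) = 0.90. With a t quantile and the stated 90% assurance on the width it is 0.83.

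I use 0.83 (unrounded 0.8347) as the residual SD of the current model. It is an upper bound.

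**2. Effect on the interval.** I use a Week 48 ANCOVA approximation to the MMRM. The current model has 5 parameters for 140 participants, so 135 residual df; two more terms leave 133. With R2 the joint share of remaining variance explained by age and DMT, beyond baseline sNfL and subtype:

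width ratio = [t(133)/t(135)] x sqrt(1 - R2) x sqrt(135/133)

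The last factor is the expected collinearity and df cost, 1.0075. The current half-width is 1.656 x 0.8347 x sqrt(2/70) = 0.2337, which gives an upper limit of 0.70 x exp(0.2337) = 0.884.

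| R2 (assumed) | Width ratio | Change in width | Upper limit at GMR 0.70 |
|---|---|---|---|
| 0 | 1.008 | +0.8% | 0.886 |
| 1% | 1.003 | +0.3% | 0.885 |
| 1.5% | 1.000 | 0 | 0.884 |
| 2% | 0.9975 | -0.3% | 0.884 |
| 5% | 0.982 | -1.8% | 0.881 |
| 10% | 0.956 | -4.4% | 0.875 |

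In randomised participants, before the df cost, 168 x (1/(1 - R2) - 1) gives about 9 at 5% and 19 at 10%.

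**3. What R2 is plausible after baseline adjustment.** Suppose age correlates 0.4 with log sNfL at both times, a marginal R2 of 16%, and r is the baseline-to-Week-48 correlation. The squared partial correlation of age given baseline is [0.4(1 - r)]^2 / [(1 - r^2)(1 - 0.16)]: 6.3% at r = 0.5, 3.4% at 0.7 and 2.1% at 0.8. Baseline sNfL therefore removes most of the age signal. All these correlations are assumed.

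**4. Simulation check.** 4,000 trials per scenario, 70 per arm, half on a DMT, with baseline sNfL in both models. The simulation has no subtype term and no dropout, so it can flatter the gain. With correlations of 0.4 (age) and 0.2 (DMT), the mean width ratio was 0.964, 0.985 and 0.997 for r = 0.5, 0.7 and 0.85. With neither prognostic it was 1.008. The largest gain was about 8% (correlations 0.5 and 0.3, r = 0.5). The unadjusted estimate was unbiased in every scenario.

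**5. Chance imbalance.** If DMT use were unrelated to subtype, with 84 per arm and 50-70% on a DMT, the SD of the imbalance would be sqrt(p(1 - p) x 2/84) = 0.077 to 0.071. The chance of exceeding 10 points would be 19% to 16%. But Protocol 3.1.1 expects the enrolled RMS participants to be stable on DMTs, so DMT use tracks the stratified subtype. As an illustration, let half be RMS and all on a DMT, and let 40% of the rest be on one (70% overall). The SD becomes sqrt(0.5 x 0.4 x 0.6 x 2/84) = 0.053 and the chance about 6%.

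The SD of the resulting shift in the estimate is sqrt(R2) standard errors: 0.14, 0.22 and 0.32 SE at R2 of 2%, 5% and 10%.

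**The case against.** The strongest case against is that nothing is wrong with the model. It adjusts for the stratification factor and for each participant's own baseline sNfL at every visit. That baseline usually averages two samples (SAP 3.1). Age is capped, and any DMT has been stable for at least 3 months, so steady effects of either should already show in baseline sNfL. That NfL responds to DMTs does not mean that stable use predicts Week 48 sNfL given baseline. A post-baseline DMT change is an intercurrent event and is not in itself a reason for a baseline covariate. Covariate choice beyond stratum and baseline outcome is a matter of judgement, and the CI already allows for chance imbalance. Age and DMT also enter the interaction models in SAP 3.2.5, and SAP 3.2.3 cannot be read.

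Most of this stands, and it is why the point is minor. Two things remain. First, participants enter without a relapse in the 8 weeks before screening (Protocol 4.2), and Protocol 2.3.3 expects DMTs to control relapses during the trial. DMT status may therefore predict later sNfL in a way that baseline cannot show. Second, the argument about DMT-related censoring is untouched by baseline adjustment of the mean, and the simulation did not test it.

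**Conclusion.** The point holds as a small improvement in efficiency and robustness, of low severity. The primary model leaves out two collected, unstratified baseline variables that the plan itself links to sNfL. Including them would probably narrow the 90% CI by about 0.3% to 4.4% for a joint R2 of 2% to 10%. There is no gain below about 1.5%, and a loss of at most about 0.8% if neither is prognostic beyond baseline. R2, the correlations, the DMT share and the residual SD are assumptions; the documents supply none of them. The MAR benefit is a matter of reasoning and has not been quantified.

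A reader might infer more than the documents support:
- That the omission biases the treatment comparison. Randomisation protects against that, and the simulated estimate was unbiased without the covariates. Dependence of dropout on DMT is a separate question that was not simulated.
- That precision is certainly being lost. That depends on what age and DMT predict beyond baseline sNfL and subtype, which the documents do not report.
- That the plan ignores both variables or has no adjusted analysis. SAP 3.2.5 uses both, and the redacted SAP 3.2.3 may contain an adjusted analysis.

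**What to change.** Before unblinding, amend SAP 3.2.2.1 to add two prespecified fixed effects to the MMRM: age (continuous) and DMT status at baseline (yes/no).

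- Define DMT status from use at first dose. SAP 5.3 defines concomitant medication as taken during the treatment period, which would make the covariate post-baseline.
- Give the DMT factor the same observed-proportion weighting in the LS means that SAP 3.2.2.1 gives the subtype strata. Without a treatment-by-DMT interaction, this affects the arm-level geometric mean ratios and not the ratio between arms.
- Carry both terms into the supplementary analysis (SAP 3.2.4) and the subgroup and interaction models (SAP 3.2.5), dropping the DMT term within DMT subgroups, where it is constant.
- Record the change in the SAP version history, which already lists covariate changes from Protocol 9.2.2.1.

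The cost is wording and two model terms, with no new data collection. The statistical downside is up to about 0.8% in CI width if neither covariate is prognostic beyond baseline.
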